8. RESEARCH QUESTION AND OBJECTIVES

The purpose of this study is to evaluate the post-discharge treatment patterns including persistence and outcomes such as recurrent VTE and bleeding among hospitalized adults with VTE treated with apixaban or warfarin.

The study objectives are to:

1. Describe the proportion of patients with VTE treated with apixaban or warfarin in the hospital
2. Understand the post-discharge treatment patterns (including persistence, switch, and discontinuation) among patients who started on apixaban or warfarin in the hospital

The secondary objective is to:

3. Assess recurrent VTE, major bleeding, and clinically relevant non-major (CRNM) bleeding among patients who continue on apixaban or warfarin in the outpatient setting while persistent on index therapy

[figure not shown]

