9.2.2. Outcome measures

The following outcome measures are assessed post-discharge, and will be measured during the variable post-index period starting on the treatment index date for the apixaban and warfarin cohorts.

Treatment patterns

- Persistent days (mean, SD, median, IQR, min, max) will be reported for patients until they discontinue, switch or end of follow-up based on definitions below
- Patients discontinuing outpatient treatment of apixaban or warfarin, respectively (NDC codes from LRx; n, %)

Note: Discontinuation will be defined as the occurrence of a ≥ 30 day gap from the run-out of days' supply of the treatment (post-discharge) index prescription (i.e. apixaban or warfarin) to the date of the next claim for the respective therapy or with no other claims for the respective therapy. The date of the discontinuation will be defined as the last day of the days' supply of the last filled prescription.

- Time (in days) from treatment index date to discontinuation date (mean, SD, median, IQR, min, max)

Note: Kaplan-Meier (KM) curves will be generated to measure median time (and 95 % CI) to discontinuation.

- Patients switching to an OAC other than apixaban or warfarin, respectively (switched) (NDC codes from LRx; n, %)

Note: Patients will be considered to have switched if they filled a prescription for OAC other than apixaban or warfarin, respectively (identified through NDC codes in LRx) or for PAC within 30 days before or after the run out date of index treatment. The date of the switch will be defined as date of the prescription of such a therapy (OAC or PAC).

- Time (in days) from treatment index date to switch date, defined as the date of the first claim for the new OAC or PAC (mean, SD, median, IQR, min, max)

Note: KM curves will be generated to measure median time (and 95 % CI) to switching

Clinical Outcomes

The following clinical outcomes will be assessed during the time patients are persistent with their respective index apixaban or warfarin treatment (treatment index):

- Patients with ≥ 1 hospitalization for recurrent VTE (ICD-10 codes in CDM; n, %)
- Incidence rate (IR) of recurrent VTE (per 100 patient years)
 - The date of the first observed event will be flagged. The numerator for IR will be the number of patients with the event of interest and denominator will be the ‘at risk’ period i.e. the time to first event. The 95% confidence intervals (CI) will also be reported.

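### Whether a VTE or bleed in a refill gap counts as on-treatment depends on what is filled afterwards; event rates are too low if events make an index refill less likely

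*Combined protocol and SAP*

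**What the plan says.** Section 9.2.2 (Outcome measures) defines discontinuation as "the occurrence of a ≥ 30 day gap from the run-out of days' supply" of the index prescription "to the date of the next claim for the respective therapy or with no other claims for the respective therapy". A gap of 1 to 29 days that ends in an index refill therefore leaves the patient persistent. Once a patient has discontinued, the date is set back to run-out: "The date of the discontinuation will be defined as the last day of the days' supply of the last filled prescription". Persistent days "will be reported for patients until they discontinue, switch or end of follow-up based on definitions below".

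A switch is a fill of another oral anticoagulant, or of a parenteral one, up to 30 days either side of run-out. It is dated at the new fill. Nothing says which date ends persistence when a patient meets both definitions.

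The persistent period also frames the clinical outcomes: recurrent VTE, major bleeding and CRNM bleeding "will be assessed during the time patients are persistent with their respective index apixaban or warfarin treatment". This matches the secondary objective in Section 8, which covers these events "among patients who continue on apixaban or warfarin in the outpatient setting while persistent on index therapy". On the incidence rate, the section says: "The numerator for IR will be the number of patients with the event of interest and denominator will be the" at-risk period, given as time to first event. It does not spell out where at-risk time ends for a patient without an event.

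Three other sections bear on this. Section 9.2, item 1d, ends follow-up at the earliest of several dates, one of them the last prescription. Section 9.6 plans Cox models for the clinical events with treatment cohort as the main effect and gives no other exposure window. Section 9.8 (Limitations) does not mention the issue.

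**The concern.** In an on-treatment analysis of first events, whether a patient is at risk on a given day should be settled by what is known up to that day. Here it is settled by later fills. Two patients with identical histories who bleed on the same gap day can be handled differently because of what happens at the pharmacy afterwards.

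This matters because the event can influence the later fill. Recurrent VTE and major bleeding are defined as inpatient stays (Section 9.2.2), while the prescription data come from retail, mail, long-term care and specialty pharmacies (Section 9.3), so an admission may itself delay an observed refill. A bleed may also be followed by stopping the index drug, and a recurrence by a change of agent. The events most likely to be dropped would then be those that ended index treatment, while the gap days of event-free patients who refill stay in person-time. All three clinical outcomes of the secondary objective rest on this rule, as does the hazard ratio for apixaban against warfarin.

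**Working it through.** The protocol gives no event rate, gap frequency or sample-size calculation, so there is no planned figure to reproduce. The rules are checked first by logic, then by a closed form and a simulation on assumed inputs.

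**Step 1. The rules applied to one event.** Take a first bleed on day 10 after run-out.

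| Next anticoagulant fill | Status under Section 9.2.2 | Persistence ends | Bleed counted? |
|---|---|---|---|
| Index drug, day 20 | Gap under 30 days, persistent | Later | Yes |
| Index drug, day 40 | Discontinued | Run-out | No |
| None | Discontinued | Run-out | No |
| Another agent, day 15, no index refill | Switched and discontinued | Day 15 or run-out, not stated | Undetermined |

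**Step 2. When this biases the rate.** Three inputs are needed, all assumed:
- s: share of counted person-time in gaps of 1 to 29 days. That these days are in the denominator is inferred from the persistence definition.
- m: event hazard in gaps relative to covered days.
- k: chance of an index refill after a gap event, divided by the chance without one.

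With the covered-day hazard set to 1:
- same window, no selection by later fills (k = 1): 1 − s + s·m
- plan's rule: 1 − s + s·m·k
- fraction lost: s·m·(1 − k) / (1 − s + s·m)

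| m | k | s = 5% | s = 10% | s = 20% |
|---|---|---|---|---|
| any | 1 | 0 | 0 | 0 |
| 1 | 0.5 | 2.5% | 5% | 10% |
| 1 | 0 | 5% | 10% | 20% |
| 2 | 0.5 | 4.8% | 9.1% | 16.7% |
| 2 | 0 | 9.5% | 18.2% | 33.3% |

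For example, s = 0.20, m = 2, k = 0.5 gives 0.20 × 2 × 0.5 / (0.80 + 0.40) = 0.20 / 1.20 = 16.7%.

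**Step 3. Simulation.** Assumptions: 400,000 patients, 30-day fills (at most 12), 5 events per 100 patient-years on covered days, 12% never refilling at each run-out, and 40% of the remaining refills preceded by a gap uniform on 1 to 29 days. Rates per 100 patient-years:

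| m | Plan, k = 1 | Plan, k = 0.5 | Plan, k = 0 | Fixed 30-day window | Covered days only |
|---|---|---|---|---|---|
| 1 | 4.96 | 4.54 | 4.32 | 5.04 | 4.98 |
| 3 | 6.47 | 5.35 | 4.30 | 7.27 | 4.98 |

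Across all the runs the covered-days rate, 5.0 by construction, came out between 4.97 and 5.11, so differences of about 0.1 are noise. At m = 1 and k = 0, if every patient who fails to refill after an event switches and the switch date governs, the plan's rate returns to 5.05.

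**Step 4. Against a covered-days rate.** The ratio is 1 − s + s·m·k, which exceeds 1 when m·k > 1. With s = 0.13, m = 3, k = 0.5 it is 0.87 + 0.13 × 3 × 0.5 = 1.065, so the planned rate would be 6.5% too high on that comparison.

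**Step 5. The hazard ratio.** If both cohorts share s, m and k, the loss cancels. If m = 1 and k = 0.4 in both, but s = 0.05 for apixaban and 0.15 for warfarin, the fractions kept are 1 − 0.05 × 0.6 = 0.97 and 1 − 0.15 × 0.6 = 0.91. A true ratio of 1.00 then appears as 0.97 / 0.91 = 1.07. With the split reversed it appears as 0.91 / 0.97 = 0.94.

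**The case against.** A reader might infer that a gap event counts only if the index drug is refilled, and that event rates must therefore be too low. The documents support neither statement.

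- **Switching.** A switch fill after run-out is dated at that fill. If that date governs, a gap-day recurrence followed by another agent is counted. This stands, but only as far as the missing precedence allows. A switcher with no further index claim also meets the discontinuation definition, with an earlier date, and a patient who fills no anticoagulant gains nothing from the switch rule.
- **Direction.** Patients who do not refill lose their gap days as well as their gap events. If events leave refilling unchanged, the rule adds no bias. This stands: the downward bias is conditional on k < 1, for which the protocol gives a plausible mechanism but no figure.
- **Size.** It is tempting to put the absolute probability of not refilling after an event in place of 1 − k. That overstates the loss. If 30% fail to refill with or without an event, s = 0.10 and m = 3 would give 0.10 × 3 × 0.3 / 1.2 = 7.5%, when the true selection loss is zero.
- **Comparator.** Against covered days the sign can reverse (Step 4). This stands, so any claim about direction must name its comparator.
- **Hazard ratio.** A reader might expect a bias against one drug. No section says which cohort has more gap time, or that post-event refilling differs between cohorts.
- **Remedy.** A fixed window adds possibly untreated days to an on-treatment outcome. It also fails if the last-prescription criterion in item 1d ends follow-up before the window opens. Both points stand and are taken up in the fix.

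None of this removes the dependence of event capture on later fills.

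**Conclusion.** The look-ahead follows directly from the definitions in Section 9.2.2, and nothing in Sections 9.2, 9.6 or 9.8 corrects it. That part is firm. The direction is conditional: rates are too low, relative to the same window without look-ahead, if an event lowers the chance of an index refill and the patient is not retained through a switch date. The size cannot be known from the documents. The range of 2.5% to 10% rests on assumed values (s from 5% to 20%, m = 1, k = 0.5). It rises to 33% at s = 20%, m = 2, k = 0, and is zero at k = 1. The apixaban versus warfarin hazard ratio is distorted only if the cohorts differ in gap time, gap hazard or post-event refilling. The point concerns the secondary objective, and the change should be made because it is cheap and removes an avoidable dependence on the future.

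**What to change.** For the clinical outcomes only, in Section 9.2.2:

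1. End at-risk time at the earliest of the event, the switch date, the end of data visibility, or run-out of the current fill plus a fixed 30 days. Apply this to events and person-time alike, in both cohorts, and use the same window in the Cox models. No later index fill then decides whether an earlier event counts.
2. State that a back-dated discontinuation does not override the switch date.
3. State in Section 9.2, item 1d, that the last-prescription criterion does not cut this window short.
4. Add a sensitivity analysis limited to days covered by supply, in both numerator and denominator.

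Keep run-out dating for the discontinuation outcome itself.

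The cost is a few sentences and a small programming change. The downside is up to 30 possibly untreated days after a true stop. If gap hazard is raised, this shows: in the simulation with m = 3 the fixed window gave 7.27 against 4.98 on covered days. The two analyses should therefore be reported side by side.

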9.1.2. Exclusion criteria

Patients meeting any of the following criteria will be excluded from the study:

1. Patients with hospitalization with a primary diagnosis of VTE in the 6-month pre hospitalization period
2. Patients with any OAC administration other than apixaban for apixaban cohort (except warfarin use before apixaban) or warfarin for warfarin cohort during hospitalization

Note: Apixaban cohort patients will be allowed to have warfarin prior to apixaban administration. At this step, we will also report the number of patients that have both apixaban and warfarin use during the hospitalization.

3. Patients with unfractionated heparin or low molecular weight heparin (LMWH) administration after apixaban (for apixaban cohort) or warfarin (for warfarin cohort) administration during hospitalization.

Note: that unfractionated heparin or LMWH prior to apixaban or warfarin will be allowed.

4. With ≥ 1 claim/record with a diagnosis code for atrial fibrillation/flutter in Dx or CDM during the hospitalization and in the 6-month pre hospitalization period
5. With ≥ 1 claim with a procedure code for mechanical heart valve in Dx or CDM during the hospitalization and in the 6-month pre hospitalization period
6. With ≥ 1 claim with a procedure code for inferior vena cava filter in Dx or CDM during the study period
7. With ≥ 1 claim with a diagnosis code or procedure code of pregnancy in Dx or CDM during the study period
8. With use of OAC or PAC (in LRx or Dx) (unless prophylactic) during the 6-month pre-hospitalization period

Note: The OAC or PAC prescription claim will be considered prophylactic if duration of the prescription is ≤ 42 days AND the start date of OAC or PAC occurs within 2 days before or 7 days after knee/hip replacement surgery

OR

Start date of OAC or PAC occurred within 7 days after the admission of a hospitalization associated with 'medically ill' (primary discharge diagnosis; codes provided separately) AND with a ≥ 3 -day length of stay of the hospitalization.

9. With data quality issues (invalid/missing enrollment dates, gender and payer type)

A preliminary attrition table will be provided to the Alliance for review, at which time modifications to the inclusion and exclusion criteria may be considered.

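### The switch rule can date a switch at a parenteral anticoagulant (PAC) fill made alongside the index drug, and it does not say which fill's run-out applies

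*Combined protocol and SAP*

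**What the plan says.** Section 9.2.2 defines a switch as a fill of a different oral anticoagulant (OAC) "or for PAC within 30 days before or after the run out date of index treatment". On timing it adds: "The date of the switch will be defined as date of the prescription of such a therapy (OAC or PAC". The bullet above that note names only an OAC; PAC enters in the note and again in the time-to-switch bullet.

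The adjacent discontinuation note uses two anchors. The gap runs from the end of the "supply of the treatment (post-discharge) index prescription (i.e. apixaban or warfarin) to the date of the next claim for the respective therapy", while the discontinuation date is the last day of the "supply of the last filled prescription". Neither is carried over to the switch rule.

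A switch has consequences beyond its own count. Persistent days "will be reported for patients until they discontinue, switch or end of follow-up based on definitions below", and "clinical outcomes will be assessed during the time patients are persistent with their respective index apixaban or warfarin treatment". Section 9.6 names treatment patterns as the primary endpoint, plans a Cox analysis of discontinuing or switching, and takes warfarin as the reference group.

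**The concern.** A patient who fills a PAC together with the index drug has not necessarily left the index drug. Nothing in the note requires index-drug fills to stop, unless that is read into the word run-out, and nothing sets concurrent fills apart. A patient still supplied with the index drug can therefore be recorded as switched on the treatment index date.

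One such record adds to the switch count, sets persistent days to zero, puts an event at time zero in the Kaplan-Meier time to switch, enters the discontinue/switch Cox model, and removes all of that patient's on-treatment time and events from the clinical outcomes.

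The mismatch between bullet and note adds a second ambiguity: the count of switchers could be built on OAC fills only while time to switch also includes PAC fills.

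The Abstract and section 7 contrast warfarin with direct oral anticoagulants that need no PAC bridging. It is a reasonable inference, not a stated fact, that concurrent PAC fills are commoner in the warfarin cohort. False switches there would raise the reference hazard and lower the apixaban-versus-warfarin hazard ratio for switching.

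**Working it through.** The plan states no figure to reproduce here, so the check applies the rule literally to constructed fill histories.

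**Inputs.** Day 0 is the treatment index date. Run-out R is the last day of supply, so a 30-day fill on day 0 has R = 29. From section 9.2.2, a PAC fill on day d is a switch if |d − R| ≤ 30. The days' supplies and fill patterns are assumed. Three readings of R are compared: first fill, most recent fill on or before d, and last fill (end of episode). The final column applies the rule proposed under fix.

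| Index-drug fills | PAC day d | First fill | Most recent fill | Last fill | Proposed rule |
|---|---|---|---|---|---|
| One 30-day | 0 | R=29, switch | R=29, switch | R=29, switch | concurrent |
| Two 14-day | 0 | R=13, switch | R=13, switch | R=27, switch | concurrent |
| Six 30-day | 0 | R=29, switch | R=29, switch | R=179, no | concurrent |
| Six 30-day | 45 | R=29, switch | R=59, switch | R=179, no | no (refill day 60) |
| Six 30-day | 95 | R=29, no | R=119, switch | R=179, no | no (refill day 120) |
| Six 30-day | 185 | R=29, no | R=179, switch | R=179, switch | switch |
| One 90-day | 0 | R=89, no | R=89, no | R=89, no | concurrent |
| One 30-day | 3 | R=29, switch | R=29, switch | R=29, switch | switch |

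Counting run-out one day later (R = 30 for a 30-day fill) changes none of these results.

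**What follows.**

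1. When the index supply ends within about 30 days, a day-0 PAC fill is a switch on every reading. With one 30-day fill, persistent days are 0. Without the PAC fill, and with no further claims, the discontinuation rule would put the end at day 29.
2. For six continuous 30-day fills the answer depends on the undefined term: 0 days on the first-fill reading, against supply to day 179.
3. With 90-day fills a day-0 PAC fill is not a switch on any reading.
4. Naming the most recent fill is not enough by itself: the day-95 row would still be a switch despite the refill on day 120. A condition on later fills is also needed.

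**Size, as an illustration only.** Let q be the share of analysed warfarin patients with a day-0 PAC fill that meets the supply condition, and s the true switching proportion, assumed to be 10%. If q is unrelated to true switching (assumed), the recorded proportion rises by q(1 − s):

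- q = 0: 0 points
- q = 1%: 0.01 × 0.90 = 0.9 points
- q = 5%: 0.05 × 0.90 = 4.5 points
- q = 10%: 0.10 × 0.90 = 9.0 points

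Without the independence assumption, the rise for any q up to 10% lies between 0 (all of these patients are true switchers) and q (none is). Mean persistent days falls by the fraction q if these patients would otherwise have average persistence (assumed), and by less if they are single-fill patients. The 18,035 warfarin patients in section 9.4 are an informational count taken before the other criteria, so q cannot be turned into a number of patients.

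**The case against.** The strongest reply is that the switch note speaks of the index treatment, where the discontinuation note speaks of the index prescription, and that section 9.6 uses index treatment for the therapy as a whole. Run-out is then the end of the episode and itself acts as the stop condition. The first-fill reading also fits the plan poorly: with 30-day fills, no PAC switch after day 59 could ever be counted, although follow-up is variable and time to switch is to be plotted. This reply largely stands. The end-of-episode reading is plausible and removes the multi-fill cases. It does not remove the short-supply cases, and the text does not choose it.

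Second, criterion 3 in section 9.1.2 already excludes "Patients with unfractionated heparin or low molecular weight heparin (LMWH) administration after apixaban (for apixaban cohort) or warfarin (for warfarin cohort) administration during hospitalization", which may remove some of the patients likeliest to fill a PAC after discharge. PAC fills before the treatment index date also fall outside the outcome window. Both points limit q. They do not make it zero, because criterion 3 concerns inpatient administration only and its note says "unfractionated heparin or LMWH prior to apixaban or warfarin will be allowed". A patient whose heparin came first in hospital, and who fills a PAC with warfarin after discharge, passes criterion 3 and then meets the switch rule.

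A reader might go on to infer that criterion 3 is itself an error, because it makes no allowance for heparin overlapping with warfarin. The documents do not support that. It is an explicit rule applied to both cohorts, with an attrition table to be reviewed before the criteria are final. Being narrower than objective 2 is true of every exclusion, and the bridging remark does not say that heparin must overlap after the first warfarin dose.

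**Conclusion.** The point holds as a defect in an endpoint definition. As written, the rule records a day-0 switch for a patient who fills a PAC with a single index fill of 30 days or less (or shorter fills that together last no longer). On the first-fill reading it does the same to continuously treated patients with fills of that length. It is worth correcting before analysis because treatment patterns are the primary endpoint and a switch also closes the on-treatment window.

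The size cannot be derived from the documents and may be small or zero; every value of q and s above is assumed. Two stronger conclusions would go too far. One is that continuously treated patients will be misclassified in general: that needs a run-out reading other than the end of the episode. The other is that the hazard ratios are biased in a known direction: the greater burden on warfarin is an inference from the bridging remark.

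Sections 4 and 9.6 also say that no cohort comparisons will be made while planning a Cox treatment effect. That is a separate issue and adds no weight here; the descriptive switch and persistence results are affected either way.

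**What to change.** In section 9.2.2:

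- Define run-out as that of the most recent index-drug fill on or before the PAC fill, and count the PAC fill as a switch only if no index-drug fill follows within run-out plus 30 days.
- Class a PAC filled on the same date as an index-drug fill as concurrent, not as a switch, and leave any later stop to the existing discontinuation rule.
- If data end before run-out plus 30 days, report these patients separately and state in advance how they are classified.
- Align the OAC-only bullet with its note, and report PAC-only switches by cohort.
- Run the rule as it now stands, with its run-out reading stated, as a sensitivity analysis.

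Record this in a protocol amendment before analysis, as section 9.6 requires for major changes to primary endpoint definitions.

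As a minor clarification, state how criterion 3 treats heparin and OAC charges on the same day, because section 9.3 says hospital charges are daily without a time stamp. Show criterion 3 exclusions by cohort in the planned attrition table.

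The cost is wording, one amendment and modest programming on claims already in hand; the 30-day look-ahead matches the discontinuation gap. Two weaknesses remain: a few true changes to parenteral therapy may be counted as continued index use, and a single-fill patient whose PAC is filled a few days after index (the last table row) still counts as a switch.

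### The switch window opens only 30 days before run-out, so a change of oral anticoagulant early in a 60- or 90-day supply is flagged late or, without a later fill in the window, never

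*Combined protocol and SAP*

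**What the plan says.** All the rules that matter here are in protocol section 9.2.2 (Outcome measures).

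- **Trigger.** "Patients will be considered to have switched if they filled a prescription for OAC other than apixaban or warfarin" (that is, other than the cohort's own drug), or for a parenteral anticoagulant (PAC), provided the fill is "within 30 days before or after the run out date of index treatment".
- **Switch date, in the note on switching.** "The date of the switch will be defined as date of the prescription of such a therapy (OAC or PAC").
- **Switch date, in the time-to-switch measure.** "defined as the date of the first claim for the new OAC or PAC".
- **Persistent days.** These "will be reported for patients until they discontinue, switch or end of follow-up based on definitions below".
- **Discontinuation.** This needs a gap of at least 30 days after run-out. "The date of the discontinuation will be defined as the last day of the days' supply of the last filled prescription".
- **Clinical outcomes.** "The following clinical outcomes will be assessed during the time patients are persistent with their respective index apixaban or warfarin treatment".

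Nothing elsewhere ends persistence when another oral anticoagulant (OAC) is filled earlier. Section 9.2, item 2, deals only with patients whose first post-discharge claim is for a different OAC. The follow-up rule in section 9.2, item 1d, does not refer to a fill of another anticoagulant.

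**The concern.** A window tied to run-out works for a 30-day fill, because it reaches back to the fill date. For a longer supply it leaves a blind period after the fill, in which the fill that makes the change does not count. A patient can then remain classed as persistent on a drug that has already been replaced.

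Two sets of results are exposed. Persistence, switching and discontinuation form objective 2, and section 9.6 treats treatment patterns as the primary endpoint. A true switch may be dated late, or counted as a discontinuation at a later date. The clinical outcomes of objective 3 are counted only while the patient is persistent. Any bleed, recurrence or person-time on the new drug inside the misclassified interval therefore enters the index drug's incidence rate and the Cox model in which treatment cohort is the main effect.

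**Working it through.** The protocol gives no figure to reproduce, so the check applies its rules day by day.

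**Inputs.** From section 9.2.2: a window of run-out ± 30 days, discontinuation dated at run-out, and persistence ended only by discontinuation, switch or end of follow-up. Assumed, because the protocol gives no days' supply: S = 30, 60 or 90 days, index fill on day 0, run-out on day S, no further index fill, and follow-up that reaches at least run-out. Taking run-out as day S − 1 moves each window by one day and changes nothing material.

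**Step 1: the blind period.** The window is [S − 30, S + 30]. A change on day t (1 to S − 1) is outside it if t < S − 30. If the switch is never flagged, the excess persistent time is S − t.

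| Index supply | Window (days) | Change days outside | Share of days 1 to S − 1 | Excess to run-out, S − t |
|---|---|---|---|---|
| 30 | 0–60 | none | 0 of 29 | none |
| 60 | 30–90 | 1–29 | 29/59 = 49% | 31–59 days, mean (31 + 59)/2 = 45 |
| 90 | 60–120 | 1–59 | 59/89 = 66% | 31–89 days, mean (31 + 89)/2 = 60 |

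**Step 2: does a later fill of the new drug fall in the window?** The rule asks only whether some fill of the other drug lies in the window, so refills count. With refills every R days, fills fall on t, t + R, t + 2R and so on.

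| Refills of new drug | 60-day index supply, change on days 1–29 | 90-day index supply, change on days 1–59 |
|---|---|---|
| None | never flagged | never flagged |
| Every 30 days | t + 30 = 31–59: flagged 30 days late | days 30–59: t + 30 = 60–89, 30 days late; days 1–29: t + 60 = 61–89, 60 days late |
| Every 60 days | t + 60 = 61–89: flagged 60 days late | t + 60 = 61–119: flagged 60 days late |
| Every 90 days | t + 90 = 91–119, beyond day 90: never flagged | days 1–30: t + 90 = 91–120, 90 days late; days 31–59: t + 90 = 121–149, beyond day 120: never flagged |

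The delays apply if the switch is dated at the fill that qualifies. If it is dated at the earliest fill of the new drug, a flagged switch could go back to day t with no delay. The two date definitions therefore give different results for the same patient.

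**Step 3: one patient.** Warfarin is filled for 90 days on day 0 and rivaroxaban on day 20; the window is days 60–120. Monthly rivaroxaban refills fall on days 50 and 80, and day 80 qualifies. A 60-day refill falls on day 80 and qualifies. A 90-day refill falls on day 110 and qualifies. With a single rivaroxaban fill nothing qualifies: the patient has 90 persistent days instead of 20 (70 in excess) and is recorded as discontinued on day 90.

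A flag that comes after run-out, such as day 110 here, leaves the patient meeting the discontinuation definition at day 90 as well. Section 9.2.2 does not say which status is then recorded.

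**The case against.** The strongest reply is that most patients who change drug keep refilling the new one. With 30- or 60-day refills every early change is eventually flagged, and the time-to-switch definition may date it correctly. This stands. A reader might infer that every early change is lost and recorded as a discontinuation, but that happens only when no fill of the new drug lands in the window. What remains is the set of never-flagged cases in the second table, and the late dating under the other definition.

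Other limits also stand:

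- A reader might turn the 49% and 66% into a share of switches missed. The documents do not support that. It would need the mix of days' supply weighted by days covered, the timing of switches within a supply, and the refill pattern of the new drug. None is given.
- A difference in error between the cohorts is possible if fill lengths differ by drug, but the protocol has no data on this.
- A reader might suppose that stockpiled early refills push run-out later and lengthen the blind period. Section 9.2.2 states no carry-over rule, so this cannot be assumed.
- Section 9.6 plans four models, which fits one combined endpoint of discontinuing or switching plus three clinical events. In a combined endpoint a switch recoded as a discontinuation is still an event, and only its date moves. The separate switch and discontinuation counts and their Kaplan–Meier curves are not protected in this way. Clinical outcomes are a secondary objective.

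**Conclusion.** The point holds in a limited form. As written, a replacement OAC filled on days 1–29 of a 60-day supply, or days 1–59 of a 90-day supply, is not itself a switch; a 30-day supply has no such gap. With 30- or 60-day refills of the new drug, the switch is recorded 30–60 days late under one date definition and possibly on time under the other.

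The switch is never recorded after a single replacement fill, with 90-day refills after any early change on a 60-day index supply, or with 90-day refills after a change on days 31–59 of a 90-day index supply. If the index drug is not refilled either, the excess persistent time is 31–59 days (60-day supply) or 31–89 days (90-day supply), with events and person-time in that interval credited to the index drug.

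These figures assume that follow-up reaches run-out; item 1d of section 9.2 can end it sooner. The front edge of the window has this gap whether run-out refers to the first index prescription or to the latest refill, which the protocol leaves open. The proportion of patients affected cannot be estimated from the documents. The change is worth making because it touches primary measures and costs little.

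**What to change.** In section 9.2.2:

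1. Define an OAC switch as the first fill of an OAC other than the index drug, from the day after the treatment index date up to 30 days after run-out of the most recent index-drug fill. The blind period is then zero for every supply length.
2. Use one switch date, the date of that first fill, in both places where the date is defined. End persistence and on-treatment clinical follow-up on that date.
3. To guard against duplicate or temporary fills, require no further index-drug fill until 30 days after run-out of the index supply in hand. A guard of only 30 days after the other fill would do almost nothing: a patient who changes on day 20 of a 90-day supply is not due an index refill until about day 90. Alternatively, report results with and without the guard.
4. State separately whether the existing window is kept for PAC fills.

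The cost is a short text change and a small amount of programming on the same prescription claims. Reported persistence may fall slightly and reported switching may rise.
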